6.6.3 Other Assessments

Baseline demographics

At the screening visit, information will be collected for date of birth, gender, ethnicity, height and weight and average weekly alcohol consumption.

6.6.4 Description of Visits and Trial Periods

Visit 1, Screening Visit

At visit 1 the following procedures and assessments will be performed:

- Subjects will receive oral and written information about the trial and be allowed to ask any questions they may have
- Subjects will sign the informed consent document
- Inclusion and exclusion criteria will be checked
- Relevant medical history will be recorded
- Concomitant medication will be recorded
- Demographic data will be recorded
- A physical examination including auscultation of heart, blood pressure and lungs will be performed by a medical doctor and safety blood samples will be collected.
- A urine pregnancy test will be performed in all women of child-bearing potential.
- Height and weight will be recorded, and BMI calculated as kg/m². Weight will be recorded with the subject wearing only light clothing and without shoes
- Subjects will receive instruction on exclusion of specified probiotic products as well as food and dietary supplements containing probiotics for the duration of the run-in and intervention period and receive a list with prohibited products
- Subjects will be instructed not to change their habitual diet and life style (physical activity level, sleep habits) during the entire course of the trial
- Subjects will be instructed to fast for 6 hours before visit 2

Run-in Period

During the run-in period (2 weeks) and in between all visits, subjects will:

- Exclude probiotic products as well as food and dietary supplements containing probiotics from their diet
- Maintain their habitual diet and life style (physical activity level, sleep habits)
- Refrain from taking any NSAIDs or other medication

Before Visit 2-5, subjects will:

- Refrain from consuming alcohol, caffeine and spicy food for 48 hours prior to visit
- Avoid strenuous exercise 48 hours prior to visit
- Fast for 6 hours before attending the visit

Visit 2-5:

- Any adverse events will be recorded
- Concomitant medication will be recorded
- Body weight will be measured with subject in light clothing and without shoes

- Collection of blood samples will be performed
- Gastroscopy procedure including clinical scoring, mucosal biopsies and obtaining luminal fluid will be performed as previously described
- Subjects will be re-instructed on exclusion of prohibited food products and supplements that apply in the period leading up to the next visit
- The subject will be randomised (Visit 2 only)
- Dispensing of ASA and trial product (Visit 2 only)
- ASA and trial product accountability will be performed as described in the trial flow chart
- Subjects will receive date and time for the next visit (Visit 2-4 only)
- The termination form in the CRF will be completed (Visit 5 only)

6.7 Endpoints

Endpoints, all exploratory:

- The effects of daily intake of Bif195 versus placebo on transcriptomics measured in ventricle and upper small intestinal mucosal biopsies obtained before and after a 4-week ASA challenge
- The effects of daily intake of Bif195 versus placebo on microbiota composition profile measured in ventricle and upper small intestinal mucosal biopsies obtained before and after a 4-week ASA challenge
- The effects of daily intake of Bif195 versus placebo on proteomics profile measured in ventricle and upper small intestinal mucosal biopsies obtained before and after a 4-week ASA challenge
- The effects of daily intake of Bif195 versus placebo on metabolomics profile measured in small intestinal luminal fluid samples obtained before and after a 4-week ASA challenge
- The effects of Bif195 versus placebo administration on the Lanza score of the ventricle obtained before and after a 4-week ASA challenge
- The effects of Bif195 versus placebo administration on the Lanza score of the duodenum obtained before and after a 4-week ASA challenge

6.8 Laboratory Analyses

6.8.1 Laboratory

All laboratory analyses will be performed at selected laboratories with respect to specific analysis. The safety blood panel is analysed in-house on the day of collection while the remaining samples will be prepared for storage by the clinical site and shipped to the appointed laboratory for analysis. The laboratory manual for the trial will provide all details on sample preparation requirements, storage requirements etc.

6.8.2 Sample Handling

Blood samples will be collected at all 5 visits. At each visit, a maximum of 25 mL whole blood will be drawn.

During the gastroscopy procedure, 6 biopsies will be taken from duodenum and 2 biopsies will be taken from the ventricle (approximately 5 mg each) at each visit.

Up to 2 ml of luminal fluid will be taken from the Duodenum during the gastroscopy procedure.

Details about the collection and preparation of blood and mucosal biopsies will be provided in the specific laboratory manual for this trial.

6.8.3 Storage of Samples at site

All blood samples, mucosal biopsies and luminal fluid samples will be listed on trial specific sample logs and stored at the clinical site during the trial.

Storage condition for blood samples is -80°C.

Storage condition for mucosal biopsies is -80°C.

Storage condition for luminal fluid samples is -80°C.

Freezers will be temperature monitored and connected to an alarm.

6.8.3 Storage of Samples at sponsor

All blood samples, mucosal biopsies and luminal fluid samples will be listed on trial specific sample logs and stored at the sponsor site in Hørsholm after the trial, while sample analysis at various labs are planned and executed.

Storage condition for blood samples is -80°C.

Storage condition for mucosal biopsies is -80°C.

Storage condition for luminal fluid samples is -80°C.

Freezers will be temperature monitored and connected to an alarm.

6.8.4 *Shipment of Samples*

Shipment of samples will be performed in accordance to the laboratory manual. The laboratory manual for the trial will provide details on shipment materials, shipment address, courier details etc.

6.8.5 *Analysis of Samples*

All samples will be analysed using validated assays and methods. Particulars about the methods used will be provided in the analytical report from the appointed laboratories and provided in the laboratory manual.

6.8.6 *Research biobank and Destruction of Samples*

A research biobank will be established in order to perform all planned analyses on mucosal biopsies, luminal fluid and blood samples described in this protocol. The described lab analyses are planned to take place in 2020 and 2021. Samples that are left after all planned analyses are performed, and all needed re-analyses are performed, will be discarded by the sponsor no later than ultimo 2022. No sample analysis will be performed that is not described in this protocol. No biological material and/or data from the trial will be shared with third-parties from this trial.

6.9 Data Management, Statistics and Quality Control

6.9.1 Data Collection and Processing

All clinical data will be collected using a CRF provided by the Sponsor. The Investigator and authorised staff at the clinical site can add data to the CRF and must keep the CRF current to reflect subject status during the course of the trial. The CRFs for any subject leaving the trial should be completed at the time of the final visit or shortly thereafter. A screening and randomisation number and the date of birth will identify the subjects on the CRF. The trial personnel must make a separate confidential record of personalised details (name and initials) on the subject identification and enrolment log which is kept separately from the CRF. Once the CRF for a subject is completed, the Investigator will approve the data and confirm the accuracy of the data recorded.

The CRFs for any subject leaving the trial should be completed at the time of the final visit or shortly thereafter. Paper source data will be shipped to Sponsor after trial closure and archived for 15 years.

6.9.2 Confidentiality

In order to maintain anonymity, subjects will only be identified by their date of birth and the assigned screening and randomisation numbers for all documents submitted to the Sponsor. Documents that will not be submitted to the Sponsor and that identify the subject (such as the signed informed consent document) must be maintained in strict confidence by the Investigator, except to the extent necessary to allow auditing and/or monitoring by the appropriate regulatory authority, the Research Associate, or Sponsor representatives. All information obtained during the trial will be handled according to local regulations and the European Directive 95/46/CE (Directive on protection of individuals with regard to the processing of personal data and on the free movement of such data).

6.9.3 Data Quality Assurance

Trial specific training of trial staff at the clinical site will be performed prior to initiation of subject recruitment by the Sponsor. The training will include as a minimum a review of all procedures to be performed at the clinical site, CRF training, blood sampling and procedures for handling mucosal biopsies and luminal fluid samples as well as accountability of trial products.

6.9.4 Audits and Inspections

The Investigators will permit auditing by the Sponsor and inspection by applicable regulatory authorities. The Investigators agree to allow the auditors/inspectors to have direct access to all trial records for review, on the understanding that the auditors are bound by professional secrecy and will respect the confidentiality of the data verified and the anonymity of the subjects.

As soon as the Investigator is notified of a future inspection by the authorities, he/she will inform the Sponsor and authorise the Sponsor to participate in this inspection.

6.9.7 Termination of Trial or Trial Site

The Sponsor reserves the right to terminate the trial at any time. Conditions that may warrant termination of the trial may include, but are not limited to, the following:

- Failure of the trial site to conduct the trial in accordance with the protocol or any other local regulations.
- Failure of the trial site to enrol subjects at an acceptable rate.
- Failure of the trial site to ensure the quality of the data collected.
- New information on the trial product, at any moment during the trial, causing doubt about the benefit/risk ratio of the trial conduct.
- A decision at the discretion of the Sponsor to discontinue the trial for any reason.

Trial termination and follow-up will be performed in accordance with the conditions set forth in ICH-GCP and local regulatory requirements.

6.9.8 Statistics and power calculation

Data will be entered into a database and analysed using statistical software. The effect of the intervention on the endpoints will be assessed using paired statistical analysis and the level of significance will be set to 0.05. Pathway analysis will also be performed using a more explorative approach.

Previous studies using the same endoscopy procedure with biopsies being analysed for arrays of gene expression have showed an approximate negative binomial distribution and a coefficient of variation of 0.344. Assuming a negative binomial distribution of the data in the present study, we have calculated that a sample size of 20 will result in a power of 0.95 for identifying genes that are down or up-regulated more than 1.5-fold as a consequence of Bif195 intervention at a significance level of 0.05. In order to achieve this statistical power, we aim to have 20 subjects completing the intervention. Assuming a drop-out rate of around 20%, we aim to randomise 25 subjects.

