6.4 Discussion of trial design

We recently conducted a clinical trial showing that oral co-administration with Bif195 can reduce the risk of low-dose ASA-induced intestinal ulceration in humans using serial VCE as our main efficacy parameter¹¹ (ClinicalTrials.gov ID number: NCT03228589).

For the present trial, we will re-use this clinical challenge model that we have already established and tested. A mild deterioration of the upper small-intestinal mucosa will be induced by ASA, a chemical agent commonly used and with well-established injurious effects on the small intestine. Based on the dataset from our previous trial, we observed that 300 mg of ASA daily for 4-6 weeks represents a relevant challenge model, both in terms of daily dose and duration, and ability to induce a mild deterioration in the small intestine as observed with VCE.

A run-in period is included to wash out the potential impact of any pre-study probiotic products. The 6 weeks between visit 3 and 4 serve the purpose as wash-out for any Bif195 effects as well as recovery of the mucosal tissue between the ASA challenge periods. A cross-over design was chosen to obtain the statistical benefits of the subjects being their own controls.

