## 5 Statistical Methodology

### 5.1 General statistical considerations

All statistical tests will be assessed using a nominal two-sided significance level of 5%.

The two treatment groups will be labelled as Bif195 and Placebo.

Weeks will be calculated as number of days divided by 7

Months will be calculated as number of days divided by 30.4375

Years will be calculated as number of days divided by 365.25

Number of days will be calculated using end date minus start date +1.

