### **5.11 Control of Multiplicity for the Primary and secondary Efficacy Analysis**

No adjustment for multiplicity is done.

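### The 0.95 power for identifying genes is a per-gene figure at unadjusted 0.05; no error-control rule covers the omics tests, and protocol and SAP differ on whether genes are tested at all

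*Protocol*

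**What the plan says.** Protocol 6.9.8 says the effect on the endpoints will be "assessed using paired statistical analysis and the level of significance will be set to 0.05". It then justifies the sample size: earlier gene-expression data "showed an approximate negative binomial distribution and a coefficient of variation of 0.344", and "a sample size of 20 will result in a power of 0.95 for identifying genes that are down or up-regulated more than 1.5-fold". That power statement uses the same 0.05 level. It gives no number of genes, read depth, within-subject correlation, false discovery rate or family-wise rule. Pathway analysis is added in a more explorative spirit.

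Protocol 6.7 lists transcriptomics, microbiota and proteomics in two tissues (ventricle and upper small intestine) and metabolomics in luminal fluid, each before and after the ASA challenge. It labels every endpoint exploratory. Protocol 6.1 has one objective, mapping the molecular mechanism.

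The SAP differs. Section 2.1 makes the Lanza score the primary objective, and section 5.10 says the biopsy data will be analysed descriptively, after unblinding. Section 5.1 sets a nominal two-sided 5% level for all tests. Section 5.11 says "No adjustment for multiplicity is done", under a heading limited to the primary and secondary efficacy analyses.

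**The concern.** A transcriptome scan tests thousands of genes at once. At 0.05 per gene, one unaffected gene in twenty is flagged by chance. Power at that threshold describes a single gene, not the quality of a list of genes. The protocol uses it for the list: it speaks of identifying genes in the plural and sizes the trial on that.

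At stake is the protocol's only stated objective. If few genes truly respond to Bif195, most of the genes flagged under the 0.05 rule would be chance findings. Pathway analysis could then start from that list, while the report carries a 95% power statement.

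**Working it through.** **Inputs.** From Protocol 6.9.8: n = 20, CV 0.344, fold change 1.5 (ln 1.5 = 0.4055), level 0.05. Two-sided testing is from SAP 5.1. Assumptions, because the documents give no figures: mean reads per gene (depth), number of genes tested, share of genes truly changed (p), and within-subject correlation (r).

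**Step 1: reproduce 0.95.** The protocol does not print its formula. The usual negative binomial approximation for a log fold change, with σ² = 0.344² + 1/depth, is

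power = Φ( ln 1.5 / √(2σ²/20) − 1.960 ).

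- Unlimited depth: σ² = 0.1183, standard error √(2 × 0.1183/20) = 0.1088, so Φ(3.727 − 1.960) = 0.961.
- Depth 200: 0.955.
- Depth 100: σ² = 0.1283, standard error 0.1133, so Φ(3.579 − 1.960) = 0.947.

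The stated 0.95 is therefore a one-gene, unadjusted figure. The formula is that of two independent groups of 20 and gives no credit for pairing.

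**Step 2: what the 0.05 rule flags.** If all genes are unaffected, 0.05 × 10,000 = 500 and 0.05 × 20,000 = 1,000 are flagged per tissue. With 500 genes it would be 25. The false share of the list does not depend on the gene count:

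false share = (1 − p) × 0.05 / [ (1 − p) × 0.05 + p × 0.95 ].

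- p = 1%: 0.0495 / (0.0495 + 0.0095) = 84%
- p = 5%: 0.0475 / (0.0475 + 0.0475) = 50%
- p = 10%: 0.045 / (0.045 + 0.095) = 32%
- p = 20%: 0.04 / (0.04 + 0.19) = 17%

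**Step 3: power at a 5% false discovery rate.** The per-gene threshold a solves

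(1 − p)a / [ (1 − p)a + p × power(a) ] = 0.05.

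The variance of the treatment contrast in one subject depends on the analysis. A post-treatment paired comparison has 2σ²(1 − r). A difference of two changes from baseline has 4σ²(1 − r). Each range below runs from depth 100 to unlimited depth, with n = 20.

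| Analysis | p = 1% | p = 5% | p = 10% |
|---|---|---|---|
| Variance that reproduces 0.95 (2σ²), normal approximation | 0.47–0.54 | 0.68–0.74 | 0.77–0.82 |
| Post-treatment paired, r = 0.5 (σ²), normal approximation | 0.94–0.96 | 0.98–0.99 | 0.99 |
| Same, paired t-test | 0.76–0.81 | 0.92–0.95 | 0.96–0.98 |
| Difference of changes, r = 0 (4σ²), normal approximation | 0.05–0.07 | 0.17–0.21 | 0.26–0.32 |

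A difference of changes with r = 0.5 has variance 2σ² and so gives the first row. With r = 0 it reaches only 0.72 to 0.75 even at unadjusted 0.05.

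The table applies r to the whole of σ². If read-count noise is instead independent between samples, the second row at depth 100 becomes 0.92, 0.97 and 0.98.

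**The case against.** The strongest reply has three parts.

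*The work is exploratory.* Protocol 6.7 labels every endpoint so, and SAP 5.10 plans no gene-level tests. This lowers the severity, since no confirmatory claim depends on the gene list. It does not remove the defect, because 6.9.8 still attaches a significance level and a power to identifying genes. It also exposes a conflict: if the SAP governs, the 0.95 refers to a test that is no longer planned; if the protocol governs, error control is missing. The false-gene counts therefore apply to the protocol's rule only. A reader might take them as the result of the SAP's plan, which SAP 5.10 does not support.

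*The cross-over gains precision.* Protocol 6.4 says "A cross-over design was chosen to obtain the statistical benefits of the subjects being their own controls", and 6.9.8 plans a paired analysis. A reader might infer that 0.95 cannot survive any error control. That is not shown: a post-treatment paired comparison with r = 0.5 keeps about 0.94 to 0.99 at a 5% false discovery rate under the normal approximation. Even with the reproducing variance, a 10% rate with 20% of genes changed gives 0.91 to 0.93. This part stands. But the endpoints are measured before and after each challenge, and an analysis of changes loses much of that gain.

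*SAP 5.11 is not about genes.* This stands too. The section covers the primary and secondary efficacy analyses (Lanza score and blood parameters), so it should not be read as a decision to leave the omics tests unadjusted. The gap rests on the protocol's single 0.05 level and on the absence of any omics rule in either document.

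**Conclusion.** The concern holds in a limited form. The 0.95 is a per-gene power at unadjusted two-sided 0.05, and neither document says what makes a gene, protein or metabolite identified once many are tested.

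Under the protocol's rule, 5% of unaffected genes are flagged. The count of 500 to 1,000 per tissue assumes 10,000 to 20,000 tested genes. The false share of 84% down to 17% assumes that 1% to 20% of genes truly change.

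Power under a 5% false discovery rate is undetermined. For 1% to 10% of genes changed it runs from about 0.05 to 0.99 across the analyses above. So the documents support neither the claim that 0.95 is lost under any error control nor the claim that it is kept.

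The protocol (paired tests at 0.05) and SAP 5.10 (descriptive) must be reconciled. This is worth correcting before the omics data are analysed. It does not call the number of subjects into question.

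**What to change.** 1. Reconcile Protocol 6.9.8 and SAP 5.10 on whether genes are tested or only described. Cover the luminal-fluid metabolomics as well, since SAP 5.10 speaks of biopsies only.
2. If they are tested, define an identified gene, protein or metabolite by a Benjamini-Hochberg adjusted p-value (for example below 0.05 or 0.10) within each tissue and omics layer. Say whether the contrast is post-treatment or a difference of changes.
3. Keep 20 completers. Restate the power at that threshold with the assumed within-subject correlation, depth and share of changed genes. Otherwise state that 0.95 applies to one pre-named gene at unadjusted 0.05.
4. If they are only described, say that the 0.95 does not describe the planned analysis, and report no gene as identified on the strength of p < 0.05.

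The cost is wording and a standard option in omics software, with no extra subjects. The downside is probably a less favourable stated power and a shorter gene list.

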6.10 Procedures for Handling Adverse Events

Adverse events (AEs) will be collected from Visit 2, the day before start of intervention with ASA and the trial product and through the end of the trial (Visit 5).

6.10.1 Definition of Adverse Events

An adverse event (AE) is any untoward medical occurrence in a trial subject administered a test product, whether considered related to the trial treatment or not. An AE can therefore be any new unfavourable and unintended sign, including abnormal laboratory findings, symptoms, or disease, or worsening of existing symptoms, which is temporarily associated with the use of a product under investigation.

6.10.2 Eliciting, Recording and Follow-up of Adverse Events

The subject will be asked if he/she has noticed any unfavourable effects when taking the investigational product. If the subject has noticed any unfavourable effects, an AE form in the CRF will be filled in for each separate AE. The form will cover onset, end, intensity, causality, action taken and outcome of the AE.

The subject must be followed-up by any clinical or biological examination considered as necessary by the medical judgment of the Investigator, until the abnormal condition is resolved, or the Investigator deems further observations or examinations to be no longer medically indicated.

6.10.3 Assessment of Intensity

The Investigator should for each AE reported by a trial subject rate the maximum intensity of the AE. The intensity grades are defined as follows:

- MILD The AE does not interfere with the subject's usual function
- MODERATE The AE interferes to some extent with the subject's usual function
- SEVERE The AE interferes significantly with the subject's usual function

Note the distinction between the seriousness and the intensity of an AE. Severe is a measure of intensity; and a severe reaction will not be classified as serious unless it meets one of the criteria for serious events listed below.

6.10.4 Assessment of Causality

The Investigator should for each AE reported by a trial subject rate the causality of the AE. The causality grades are defined as described in Table 3.

Table 3 Assessment of causality of adverse events

For causality classification, all criteria of a category have to be met.

Definite	An AE occurring in a plausible time relationship to test product administration, and which cannot be explained by concurrent disease or concomitant drugs or chemicals. The response to withdrawal of the product (de-challenge) should be clinically plausible, and the AE should recur on re-challenge.
Probable	An AE with a reasonable time sequence to administration of the test product, unlikely to be attributed to concurrent disease or concurrent drugs or chemicals, and which follows a clinically reasonable response on withdrawal (de-challenge). Re-challenge information is not required to fulfill this definition.
Possible	An AE with a reasonable time sequence to administration of the test product, but which could also be explained by concurrent disease or concomitant drugs or chemicals. Information on drug withdrawal may be lacking or unclear.
Unlikely	An AE with a temporal relationship to administration of test product which makes a causal relationship improbable, and in which concomitant drugs, chemicals or underlying disease provide plausible explanations.
Unrelated	An event which has clearly and incontrovertibly no temporal relationship to the test product or is due to underlying/concurrent illness or effect of a concomitant drug.

